It should be noted that these outcomes are comparable to those reported in the literature for percutaneous SFA interventions.

Table 8: STP 115 Safety Outcomes

Safety Outcomes	30-Day Treated Subjects N = 59 ¹	6-Month Treated Subjects N = 59 ¹	12-Month Treated Subjects N = 35
Major Adverse Events (MAE)², (% n/N)	3.4% (2/59)	10.2% (6/59) ⁶	14.3% (5/35)
Major Adverse Clinical Events (MACE)³, (% n/N)	3.4% (2/59)	10.2% (6/59) ^{6,7}	14.3% (5/35)
Deep Vein Thrombosis (DVT)⁴, (% n/N)	0% (0/59)	0% (0/59)	0% (0/35)
Major Bleeding⁵, (% n/N)	0% (0/59)	0% (0/59)	0% (0/35)

¹ Excludes 1 subject who did not receive an implant and withdrew from the study post-discharge.

² Composite endpoint defined as death, target limb amputation and target vessel revascularization as adjudicated by Independent Medical Review.

³ Composite endpoint defined as death, target limb amputation, TVR, DVT of ipsilateral limb or bleeding event requiring transfusion > 2 units of packed red blood cells as adjudicated by Independent Medical Review.

⁴ Defined as a symptomatic blood clot (thrombus) in the ipsilateral limb as adjudicated by Independent Medical Review.

⁵ Defined as transfusion of >2 units packed red blood cells (PRBC) through discharge as adjudicated by Independent Medical Review.

⁶ All subjects experienced target vessel revascularizations (TVR).

⁷ One subject experienced 2 events (TVR and acute limb ischemia).

Comparison of MAE Rates at 30 days and 12 Months to the Viabahn Stent Graft

MAE, defined similarly to the PQ Bypass study (all cause death, TVR and amputation of index limb) through 30 days and 12 months for the Viabahn Endoprosthesis, as reported in the literature, are presented below in **Table 9** and **Table 10**. Only studies which reported all individual events included in the MAE composite were included, so a sum total MAE rate could be calculated.

MAE rates in studies which reported on the Viabahn stent graft ranged from 0.0% to 11.1% at 30 days and from 32.5% to 50.0% at 12 months.

Table 9: Comparison of PQ Bypass 30 Day MAE Rates to Viabahn 30 Day MAE Rates as Reported in the Literature

Lead Author - Year	30 Day Death (%)	30 Day TLR/TVR (%)	30 Day Amputation (%)	Total 30 Day MAE ¹ (%)
Schneider_2011 ¹	0.0%	7.4%	3.7%	11.1%
Saxon_2013 ²	0.0%	0.8%	0.0%	0.8%
Lammer_2013 ³	0.0%	1.3%	0.0%	1.3%
Zeller_2014 ⁴	0.0%	0.0%	0.0%	0.0%
PQ Bypass Study	0.0% (0/59)	3.4% (2/59)	0.0% (0/59)	3.4% (2/35)

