5.2 Study Endpoints

Primary Safety Endpoint:

The primary safety endpoint for this study is freedom from a major adverse event (MAE) at 30 days post procedure. An MAE is defined as TLR, amputation of the treated limb, or death.

Primary Effectiveness Endpoint:

The primary effectiveness endpoint is defined as stent patency as evidenced by a peak systolic velocity ratio (PSVR) < 2.5 from DUS obtained within the 12 month visit window with no clinically driven re intervention within the stented segment.

Secondary Safety Endpoints:

Secondary safety endpoints will be evaluated and include:

1. The combined rate of death at 30 (± 7) days, target lesion revascularization (TLR), index limb amputation, and an increase in Rutherford Becker Classification by 2 classes (comparing pre to post procedural assessments) at 12 months.
2. Major adverse vascular event (MAVE) at 30 days, 6 months (180 ± 14 days) and 12 months (360 ± 30 days) defined as stent thrombosis, target limb amputation, clinically apparent distal embolization, defined as causing end organ damage (e.g. lower extremity ulceration, tissue necrosis, or gangrene), procedure related arterial rupture, acute limb ischemia, or bleeding event requiring transfusion.
3. The combined rate of serious procedural adverse events, including death, myocardial infarction, index limb amputation, and access site and treatment site complications requiring surgery, blood transfusion (>2 units of PRBC), or prolonged hospital stay within 30 days of the index procedure.

Secondary Effectiveness Endpoints:

1. Acute technical (lesion) success, procedural success and device success.
2. Ankle Brachial Index (ABI) and Toe Brachial Index (TBI) at 1, 6 and 12 months.
3. Target vessel revascularization (TVR) at 6 and 12 months.
4. Limb ischemia by Rutherford Becker Classification at Baseline, 1, 6, and 12 months.
5. Number of any type of index limb amputations at 6 and 12 months.
6. Absolute Claudication Distance as measured by the Exercise Tolerance Test (TASCI) assessed in 100 subjects at baseline, 1, 6, and 12 months.
7. Target lesion revascularization (TLR) at 1, 6 and 12 months.

8. The rate of primary assisted patency through follow up defined as: revascularization of non occlusive (<99%) stenosis within the stent graft or immediately above or below the treated arterial segment with less than 50% residual stenosis.

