9. The rate of secondary patency through follow up defined as: revascularization of occlusion (100%) within the stent graft or immediately above or below the treated arterial segment with less than 50% residual stenosis.

Additional Secondary Endpoints:

The following additional endpoints will also be reported:

1. A combined rate of death at 30 days, or TLR, index limb amputation, and an increase in Rutherford Becker Classification by 2 classes (comparing pre to post procedural assessments) measured at 24 months.
2. Target vessel revascularization (TVR) at 24 months post procedure.
3. Limb ischemia improvement by Rutherford Becker (improvement in scale by ≥ 1) at 24 months.
4. Major Adverse Vascular Event (MAVE) by 24 months, defined as: Stent thrombosis, target limb amputation, or clinically apparent distal embolization, defined as causing end organ damage (e.g. lower extremity ulceration, tissue necrosis, or gangrene).
5. Procedure related arterial rupture, acute limb ischemia, or bleeding event requiring transfusion. Number of any type of index limb amputations at 24 month follow up. Target lesion revascularization (TLR) at 24 months post procedure.

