- **TIA** - A neurological deficit lasting less than 24 hours and, if an imaging study is performed, shows no evidence of infarction. These events may occur anytime throughout a subject's study participation and may or may not require intervention.

Stent Graft Occlusion

Complete blockage of blood flow through the Stent Graft as determined by traditional imaging (e.g. DUS, CTA, MRA or Angiography).

Stent Graft Placement Accuracy

Estimated distance (mm) from the operator's intended target as compared to the actual position placed as assessed via angiography during the index procedure.

Target Lesion Revascularization (TLR)

A re intervention of the index lesion site.

Target Vessel Revascularization (TVR)

Treatment of another lesion at the target vessel site but no the index lesion itself.

Technical Success, Acute

Successful delivery of PQ Bypass Stent Graft System to the identified area and successful removal of delivery system.

Unanticipated Adverse Device Effect (UADE)

An adverse device effect which by its nature, incidence, severity or outcome has not been identified in the risk analysis report.

Vascular Access Type

Method of entry into the vascular system. Categorized as either surgical cut down or percutaneous.

20.0

REFERENCES

- ¹ American Heart Association. What is PAD? Available at: http://www.heart.org/pr nt_presenter.jhtm ? dent f er=3020249. Accessed June 3, 2013.
- ² National Institutes of Health. National Heart, Lung, and Blood Institute. Diseases and Conditions Index. What is Atherosclerosis? Available at: <http://www.ncbi.nlm.nih.gov/health/conditions/atherosclerosis/WhatIs.htm>. Accessed June 3, 2013.
- ³ Chi Y and Jaff M. Optimal risk factor modification and medical management of the patient with peripheral arterial disease. *Catheterization and Cardiovascular Interventions*. 2008;71(4):475-89.
- ⁴ Bashir R and Cooper C. Evaluation and medical treatment of peripheral arterial disease. *Current opinion in cardiology*. 2003;18(6):436-43.
- ⁵ Gornik H and Beckman J. Peripheral Arterial Disease. *Circulation*. 2005;111:e169-e172.
- ⁶ Alber M, Romiti M, Brochado-Neto FC, et al. Meta-analysis of alternate autologous veins bypass grafts to infrapopliteal arteries. *J Vasc Surg*. 2005;42:449-55.
- ⁷ TASC Classification Consensus Document on PAD – 2000.

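### TVR is defined to exclude the index lesion, so it omits stent-graft re-treatment, can fall below TLR, and leaves no per-subject rate of any target-vessel re-intervention

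*Combined protocol and SAP*

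**What the plan says.** Section 19 gives two adjacent definitions. TLR is "A re intervention of the index lesion site". TVR is "Treatment of another lesion at the target vessel site but no the index lesion itself", where the second negative is evidently a slip for 'not'. No other section of the supplied text gives an inclusive definition of TVR.

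Section 5.2 lists both as endpoints: secondary effectiveness item 3 is "Target vessel revascularization (TVR) at 6 and 12 months" and item 7 is "Target lesion revascularization (TLR) at 1, 6 and 12 months". Among the additional endpoints, item 2 is "Target vessel revascularization (TVR) at 24 months post procedure", and TLR at 24 months appears in item 5. The primary safety composite uses TLR and not TVR: "An MAE is defined as TLR, amputation of the treated limb, or death". Section 11.1 plans only point estimates, numbers of subjects and 95% confidence bounds for the remaining secondary endpoints.

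Section 2.3 reports STP 115. The MAE footnote to Table 8 reads "Composite endpoint defined as death, target limb amputation and target vessel revascularization as adjudicated by Independent Medical Review", with no TLR term. The literature on the marketed stent graft is introduced as "MAE, defined similarly to the PQ Bypass study (all cause death, TVR and amputation of index limb", and Tables 9 and 10 show revascularization in a single column headed TLR/TVR.

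**The concern.** A reader who meets the label TVR will usually take it as the vessel-level measure: any repeat revascularization of the treated artery, with TLR as a subset. Under Section 19 it is the complement instead. A subject whose graft is re-opened has a TLR and no TVR.

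Two things follow. First, the plan reports two parts of vessel-level re-intervention but never the whole, counted once per subject. Second, the same three letters seem to mean something else in Section 2.3 of the same document, so this trial's TVR could be read against figures that measure a different quantity. What is at stake is the description and interpretation of a secondary endpoint, not the trial's success decision.

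**Working it through.** **Figures in the protocol.** Tables 8 to 10 give these revascularization counts for STP 115:

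- 30 days: 2/59 = 3.4%.
- 6 months: 6/59 = 10.2%. A footnote to Table 8 says that all six subjects had TVR.
- 12 months: 5/35 = 14.3%. Table 10 shows 0/35 deaths and 0/35 amputations, so all five are revascularizations.

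All three percentages reproduce.

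**Definitions side by side.** Let L be the set of subjects with re-intervention at the index lesion and O the set with re-intervention elsewhere in the target vessel.

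- Section 19 TLR = L.
- Section 19 TVR = O.
- Vessel-level rate = L or O = L + O − (both).

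The last line is not a planned output. From the two reported rates it can only be bounded: at least the larger of TLR and TVR, at most their sum.

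**Illustration at the planned 60 evaluable subjects.** The documents do not say what share of re-interventions falls at the index lesion, so the split is an assumption and is varied. Suppose 9/60 (15.0%, close to the 14.3% in STP 115) have some target-vessel re-intervention and no subject has both kinds:

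| At index lesion (TLR) | Elsewhere (TVR, Section 19) | Any target vessel |
|---|---|---|
| 4/60 = 6.7% | 5/60 = 8.3% | 9/60 = 15.0% |
| 7/60 = 11.7% | 2/60 = 3.3% | 9/60 = 15.0% |
| 8/60 = 13.3% | 1/60 = 1.7% | 9/60 = 15.0% |
| 9/60 = 15.0% | 0/60 = 0% | 9/60 = 15.0% |

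Without overlap, TVR is below TLR as soon as more than half of the revascularized subjects are treated at the index lesion, and it is 0% if all are. An inclusive TVR stays at 15.0% in every row and can never be below TLR.

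**Overlap.** Take the second row's reported rates, TLR 7/60 and TVR 2/60, and drop the no-overlap assumption. The vessel-level rate is then anywhere from 7/60 = 11.7% (both TVR subjects also had TLR) to 9/60 = 15.0% (neither did). A reader of the two rates alone cannot tell which.

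**Is Section 2.3 inclusive?** The STP 115 composite has TVR as its only revascularization term. Read with the Section 19 meaning, re-treatment of the graft itself would not count as an MAE in that study, which is hard to credit. The pooled TLR/TVR column points the same way. This is an inference: the supplied text names TVR for STP 115 but does not define it, and the literature definitions are not shown either.

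**Possible gap.** If all STP 115 events were at the treated segment, the Section 19 definition would report 0% for them. If none were, it would report the full rate. The possible difference is therefore 0 to 10.2 points at 6 months and 0 to 14.3 points at 12 months. The documents narrow it no further.

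**The case against.** The strongest reply is that Section 19 sets out an explicit, pre-specified split into two disjoint event types and that both are reported. TLR is an endpoint at 1, 6, 12 and 24 months, which covers every TVR time point, so a re-treated graft is counted, only under the other label. TVR below TLR is then an ordinary result of the split, not an error. No section says that TVR in this trial was meant as the vessel-level total, and the exact combined rate could be computed from subject-level data on request. All of this stands, and it keeps the point minor.

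A reader might go further and infer that this trial's TVR is to be judged against the Section 2.3 rates and would look favourable there only because the definition changed. The documents do not support that. Tables 9 and 10 compare STP 115, not this trial, with a marketed stent graft. The only pre-specified benchmark here is the 70% patency goal, and TVR is analysed descriptively. The STP 115 definition is not shown, so a change of definition is not established. Nor would definition be the only reason for a difference: STP 115 routes the graft through the vein around lesions averaging 28.6 cm, 93.3% of them TASC D, whereas this trial stents 8 to 18 cm TASC B and C lesions in place.

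The reply leaves three things unanswered: no per-subject vessel-level rate is planned, the sum of the two rates does not give it, and one label appears to carry two meanings in one document.

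**Conclusion.** The point holds as a cheap improvement to a secondary endpoint. Under Section 19, TVR excludes index-lesion re-intervention, can be lower than TLR, and leaves the rate of any target-vessel re-intervention per subject unreported. This follows from the wording alone.

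The further statement, that a reader setting this trial's TVR beside the Section 2.3 figures could be misled, rests on the inference that those figures include the treated segment. The gap could be anything from none to the whole vessel-level rate. At an assumed 15.0% vessel-level rate in 60 subjects without overlap, Section 19 TVR would run from 8.3% down to 0% as the number treated at the index lesion rises from 4 to 9 of the 9 revascularized subjects.

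The documents do not support reading this as hidden graft failures, since TLR is reported alongside. They also do not support reading it as a threat to the trial's conclusions: primary safety uses TLR, and primary effectiveness uses duplex ultrasound and re-intervention within the stented segment. Sample size, alpha and the success rule do not involve TVR.

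**What to change.** In Section 19, define TVR as any re-intervention in the target vessel, including the index lesion, counted once per subject. If the present quantity is still wanted, report it in addition under the name non-target-lesion TVR. The endpoint lists in Section 5.2 and the protocol summary can stay as they are, since they use only the label.

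The cost is one definition sentence and possibly one table row, using events already collected for TLR and TVR. The downside for the sponsor is that the reported TVR rate will be equal to or higher than under the current wording.

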May not be reproduced without written permission from PQ Bypass, Inc.

- ¹ Use of retrospective assessments, prior to signing of informed consent, were used if they were performed as routine standard of care
- ² Brief physical examination at baseline was targeted to assess limb schema and concurrent medical conditions to assess subjects' eligibility for study participation. Health status assessments were performed at discharge and subsequent clinical visits to assess for limb schema and other changes in medical conditions that are reportable as adverse events
- ³ CK at discharge time point was obtained only if subject shows signs or symptoms of cardiac schema. CK MB levels required for CK to be elevated ($\geq 2X$ the laboratory upper limit of normal) if CK and CK MB were elevated, and acute myocardial infarction was diagnosed, the subject will be treated according to hospital procedures
- ⁴ 30 day ECGs performed if subject experiences any schema symptoms since discharge
- ⁵ Angiography performed both pre procedure and post procedure to record data needed for percent diameter stenosis and other measures. Additional angiography may be performed at investigator discretion or to assess events
- ⁶ Duplex ultrasound to be completed at each visit
- ⁷ At baseline Category Scale, during follow-up, both Clinical Category and Clinical Improvement Rutherford Becker Scores
- ⁸ Perform Toe Brachal Index (TBI) only if unable to reliable assess ABI reading. Tests are performed in resting state. Post procedure follow-up assessments depend on which test was performed pre procedure
- ⁹ Pavulox recommended for one year post procedure; ASA is recommended for all subjects indefinitely

Patient Screening, Enrollment and Follow-Up

¹ If procedure rescheduled, final eligibility (e.g., labs, imaging) will need to be reconfirmed.

Change History

Revision Letter	Change Description
A	Initial Release
A1	Amendments per Austrian EC requests
B	
 • Lesion length adjustment • Clinical outcome data update • Device description update • Statistical Plan update from 30 to 60 evaluable patients • Risk benefit update • Addition of x-ray at 12 month follow-up • Minor editorial updates
B1	Added "Section 18 PUBLICATIONS" as requested by Latvian Authorities
B2	Updated statistical plan rationale per Italian EC request using superiority hypothesis instead of a non-inferiority

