Study Enrollment	12-month enrollment period: 
 • Initial enrollment: Proposed Q4, 2014 • Last enrollment: Proposed Q3, 2015 	
Study Duration	36 months (12-month enrollment and 24-month follow-up)	
Primary Safety Endpoint:	Major Adverse Clinical Events (MACE) at 6 months. MACE is a composite endpoint defined as: 
 1. Death 2. Target limb amputation 3. Target vessel revascularization (TVR) 4. Major bleeding (transfusion of >2 units PRBC) 5. Deep vein thrombosis on ipsilateral limb 	
Primary Performance Endpoint:	The rate of primary patency at 6 months. Primary patency defined as: no evidence of clinically significant stenosis ($\geq 50\%$) within the stent graft or immediately above or below the treated arterial segment based on duplex ultrasound (systolic velocity ratio of >2.5). The primary effectiveness endpoint will be assessed by an independent Core Lab.	
Secondary Safety Endpoints:	Major Adverse Clinical Events (MACE) will be evaluated at: 
 1. Discharge 2. 12 months 3. 18 months 4. 24 months 	
Secondary Effectiveness Endpoints:	
 • Technical Success defined as: successful delivery, access and placement of the investigational devices and successful removal of delivery system. • Procedural Success defined as: successful delivery, access and placement of the investigational devices in the absence of in-hospital MACE. • Clinical Success defined as improvement of at least one category using the Rutherford Clinical Severity Scale through follow-up. • The rate of primary assisted patency through follow-up defined as: revascularization of non-occlusive ($<99\%$) stenosis within the stent graft or immediately above or 	

	
below the treated arterial segment with less than 50% residual stenosis.
 
 The rate of secondary patency through follow-up defined as: revascularization of occlusion (100%) within the stent graft or immediately above or below the treated arterial segment with less than 50% residual stenosis.

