3.0 DEVICE / TECHNOLOGY DESCRIPTION

3.1 Introduction

PQ Bypass designs and manufactures the PQ Bypass Stent Graft System (SGS). The SGS is comprised of a Stent Graft and a Stent Graft Delivery System and is intended to place stent grafts in the peripheral vasculature to improve blood flow.

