3.5 Mechanism of Action

The PQ Bypass Stent Graft System delivers an individual Stent Graft via a manual catheter delivery system.

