5.5 Inclusion Criteria

The subject must meet all of the following criteria at the time of eligibility:

1. Age ≥ 18 years and of age of legal consent.
2. Women of child bearing potential must have a negative pregnancy test within 7 days prior to the index procedure.
3. Subject has lifestyle limiting claudication or rest pain (Rutherford Becker scale 2-4*) with a resting ABI < 0.9 . Resting TBI is utilized only if unable to reliably assess ABI. TBI must be < 0.7 . These assessments are required for the target limb, but both limbs are preferred.
4. A superficial femoral artery lesion with $> 50\%$ stenosis or occlusion which requires treatment.

5. Stenotic lesion(s) or occluded length within the same vessel (one long or multiple serial lesions) $\geq 80\text{mm}$ to $\leq 180\text{mm}$.
6. Reference vessel diameter (RVD) $\geq 5.0\text{mm}$ and $\leq 6.7\text{ mm}$, angiographically/CTA/MRA defined.
7. Patent popliteal artery 3 cm proximal to tibial plateau
8. At least 1 patent tibial artery to the foot (<50% stenosis)
9. The target lesion(s) can be successfully crossed with a guide wire and dilated.
10. Adequate aortoiliac or common femoral "inflow" is defined as <30% stenosis after either PTA or stenting of the inflow lesion. After treatment of the inflow lesion, the residual pressure gradient across the target lesion will be obtained and if the peak to peak pressure gradient is < 20mmHg, the subject will be included in the study. Subjects enrolled with aortoiliac or common femoral artery lesions resulting in poor inflow, must be treated prior to receiving the study treatment. (Same Day or earlier)
11. If a subject has bilateral obstructive SFA disease, only 1 leg may be treated with the investigational device in the study.
 - a. If the study leg is treated first, the contra lateral procedure should not be performed until at least 30 days after the index procedure (staged); and should only be performed with an approved (CE Marked) device.
 - b. If the contra lateral leg is treated with an approved (CE Marked) device prior to treatment of the study leg, treatment of the contra lateral leg should be performed at least 15 days prior to the treatment of the study leg.
12. The subject is eligible for standard surgical repair, if necessary.
13. A subject who requires a coronary intervention should have it performed at least 30 days prior or 30 days post the treatment of the target lesion.
14. Subject must provide written informed consent.

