11.2 Primary Safety Endpoint Reporting

The primary safety endpoint is the rate of Major Adverse Events (MAEs) at 30 days. The number and percent of subjects that experience at least one MAE through 30 days post procedure will be reported along with the upper one sided 95% confidence limit. In addition the number and percentage of subjects reporting MAEs and MAVEs will be presented using descriptive statistics at various time intervals, combined and by type of event. The confidence intervals will be calculated using the Wilson method.

11.3 Primary Performance Endpoint Reporting:

The primary performance hypothesis will be tested by calculating the one sided 95% lower confidence limit for the rate of successful performance using the Wilson Method. If the lower limit exceeds the performance goal rate of 70% the null hypothesis will be rejected and the endpoint will be met. In addition to hypothesis testing, descriptive statistics of the primary performance endpoint will include the total number and percentage of patent PQB grafts.

11.4 Secondary Endpoint Analysis:

The secondary endpoint of primary assisted and secondary patency will be summarized using Kaplan Meier survival analysis. Life tables will be created and a Kaplan Meier survival curve will be presented.

The secondary endpoints inclusive of Procedural Success, Clinical Success and Technical Success will be summarized by providing point estimates, number of subjects, and 95% confidence bounds calculated using the Score approximation.

11.5 Demographic, procedural and safety data:

Demographic and baseline clinical and disease characteristics will be summarized in tables. For continuous variables the summary will include number, mean, and standard deviation and 95% confidence intervals. Summaries for categorical variables will include the number and percent of subjects in each category.

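### Acute technical (lesion) success has no lumen criterion, so a subject left with more than 50% stenosis still counts as a lesion success

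*Combined protocol and SAP*

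**What the plan says.** The first secondary effectiveness endpoint, in the Protocol Summary and in Section 5.2, is "Acute technical (lesion) success, procedural success and device success". Section 19 sends the reader from *Acute Technical Success* to *Technical Success, Acute*, which reads "Successful delivery of PQ Bypass Stent Graft System to the identified area and successful removal of delivery system". In the public text that is the only definition of the term for this trial (STP 185).

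Other parts of the protocol bear on it:

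- **Intended use (Section 4.0):** to improve luminal diameter.
- **Entry severity (Section 5.5, item 4):** an SFA lesion with more than 50% stenosis or "occlusion which requires treatment".
- **Data collected (Schedule of Assessments, footnote 5):** angiography before and after the procedure "to record data needed for percent diameter stenosis and other measures".
- **Reading of images (Protocol Summary, Core Imaging Laboratory):** an independent duplex and angiographic core laboratory.
- **Analysis (Section 11.4):** "The secondary endpoints inclusive of Procedural Success, Clinical Success and Technical Success" are summarised by point estimates, numbers of subjects and 95% bounds, with no hypothesis test.

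**The concern.** The word *lesion* in the endpoint's name promises a result about the lesion, and the device is meant to widen the lumen. The definition asks only whether the system got there and whether the delivery part came out. It says nothing about what the angiogram shows afterwards. A subject can finish the procedure still meeting the stenosis criterion that made the lesion eligible and be recorded as a lesion success.

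At stake is how the acute effectiveness result is read. A high rate would be taken as evidence that lesions were opened, when it would only show that the system could be delivered and its delivery part withdrawn. The percent diameter stenosis that could answer the question is collected but is not tied to this endpoint.

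**Working it through.** The plan gives no figure for this endpoint, so there is none to reproduce. The check is of wording, followed by a simple scale.

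**1. Apply the rule to the possible acute outcomes.** The last column uses the form proposed under the fix, with 50% as the threshold.

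| Acute outcome | Current Section 19 rule | With placement and lumen criterion |
|---|---|---|
| Graft in place, delivery system out, residual stenosis below 50% | success | success |
| Graft in place, delivery system out, residual stenosis above 50% | success | failure |
| Graft not released, whole system withdrawn | not stated; better read as failure | failure |

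The second row is the defect. It follows directly from the definition and needs no interpretation.

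**2. Is placement of the graft required?** Section 3.1 says "The SGS is comprised of a Stent Graft and a Stent Graft Delivery System", and Section 3.5 says "The PQ Bypass Stent Graft System delivers an individual Stent Graft via a manual catheter delivery system". Delivery of the system can therefore be read to include the implant. Only the delivery system has to be removed, which suggests that the graft stays. By contrast, the technical success definition in the STP 115 summary (Section 2.3, Table 5) is "successful delivery, access and placement of the investigational devices and successful removal of delivery system". The word *placement* is in that definition and not in the STP 185 one. Placement is implied here but not stated.

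**3. Does another definition fill the gap?** Section 19 is alphabetical and has no entry for device success or procedural success. A residual stenosis limit of less than 50% does appear in Section 5.2, items 8 and 9, but it applies to re-interventions counted under assisted and secondary patency, not to the index procedure. Section 11.4 names Clinical Success, which is not in the STP 185 endpoint list; a definition appears only in the STP 115 summary, as Rutherford improvement.

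**4. Scale.** Let k be the number of subjects, among N, with the graft in place but residual stenosis above the threshold. Then

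current rate − revised rate = k / N.

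With N = 60 evaluable subjects:

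- k = 1: 1/60 = 1.7 points
- k = 2: 2/60 = 3.3 points
- k = 3: 3/60 = 5.0 points

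If all 65 permitted subjects were enrolled and counted, one subject would be 1/65 = 1.5 points. The documents give no value for k, so these figures show the effect per subject and are not a forecast.

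**The case against.** The strongest defence is that the second row of the table should be rare. Inclusion item 9 and Section 6.2 have the lesion crossed and dilated before the study device goes in, and Section 8.2 adds balloon dilation inside the graft after placement. The lumen result is also recorded elsewhere: percent diameter stenosis on the procedural angiogram, duplex ultrasound from discharge onwards, and the 12-month velocity-ratio primary endpoint. Whether technical success should carry a lumen threshold is a design choice, and the 50% figures in the protocol were set for entry and for re-intervention, not for completion of the index procedure.

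Most of this stands. It limits the likely size of the problem and means that 50% cannot be presented as the protocol's own completion criterion. It does not remove the mismatch: the definition allows the outcome, and the endpoint carrying the lesion label is the one that ignores it.

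A reader might draw stronger conclusions that the documents do not support:

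- **That a graft never released counts as a success.** This is a strained reading. The system includes the graft, and only the delivery part has to come out. The absence of the word *placement* justifies a clarification and no more.
- **That device success has no planned analysis because Section 11.4 does not name it.** Section 11.1 covers other secondary endpoints with point estimates and Score bounds.
- **That technical success is indistinguishable from device success.** Device success is undefined in the public text, so the two cannot be compared.

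**Conclusion.** The point holds. As written, acute technical (lesion) success includes subjects whose post-procedure stenosis still exceeds 50%, so it cannot show whether the device improved luminal diameter. The non-naming of graft placement is a lesser ambiguity in the same sentence.

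The size is 1.7 percentage points for each such subject among 60. How many there would be is unknown. A reader might infer that the rate will sit near 100% whatever the angiogram shows, but no figure in the documents supports that prediction.

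The consequence is confined to one part of a secondary, descriptive endpoint. The primary patency test, the sample size and the primary safety endpoint do not depend on it. The change is worth making because it is cheap and uses data already being collected, not because the trial's main conclusion is at risk. The missing definition of procedural success and the stray Clinical Success are matters of detail to settle in the same edit.

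**What to change.** In Section 19, define acute technical (lesion) success by three conditions: the graft is placed at the intended site; the delivery system is removed; and residual diameter stenosis is below a pre-specified threshold on the final procedural angiogram, as read by the angiographic core laboratory. A 50% threshold would be consistent with entry item 4 and with endpoint items 8 and 9. The sponsor may choose another value if it is justified before the data are seen.

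The present delivery-and-removal measure, with placement named, can be kept as device success, so that nothing now reported is lost. In the same revision, define procedural success and reconcile Clinical Success in Section 11.4 with the STP 185 endpoint list, either by removing it or by adding it with a definition.

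The cost is wording. The post-procedure angiogram, its percent diameter stenosis and the core laboratory are already in the plan. The downside is that the reported lesion success rate may be slightly lower than under the present rule, by 1.7 points for each of 60 subjects reclassified.
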